## Induction Phase (Cohort 2)

- For JNJ-3989: (Total number of injections received/ 9) \* 100%

## Consolidation Phase

- For JNJ-3989: (Total number of injections received/ 3) \* 100%
- For PegIFN- $\alpha$ 2a: (Total number of injections received/ 12) \* 100%

## 5. EFFICACY

All efficacy data will be analyzed by cohort, combined cohort and overall, analysis phase and over time (when applicable). The primary analysis set will be the ITT analysis set for the primary efficacy endpoint, and the Treated analysis set for the rest efficacy endpoints. A secondary analysis set (combined cohort) will be performed combining the data from participants who received PegIFN- $\alpha$ 2a but not JNJ-6379 in Cohort 1 with data of Cohort 2 by analysis phase, the PegIFN- $\alpha$ 2a ITT analysis set will be used. This combined cohort is for the selected efficacy endpoints. The mTreated, mITT, and mPegIFN- $\alpha$ 2a ITT will be used if relevant difference between the sets exist (see Section 2.3). Selected efficacy endpoints will be also analyzed using the PP analysis set (see definition in Section 2.3). Efficacy assessments over time will be performed at the analysis time points defined in Section 2.1.

### 5.1. Analysis Specifications

All efficacy endpoints will be summarized descriptively by analysis phase, cohort, combined cohort and overall. In general, continuous variables will be summarized using descriptive statistics

including the number of participants, mean, standard deviation (SD), standard error (SE), confidence interval (CI), median, and range. The confidence level is detailed in Section 5.1.1. Binary or categorical variables will be summarized using the number and percentage of participants in each category. For time-to-event variables, a summary table including number of participants included in the analysis, number of participants censored, 25th and 75th percentiles and median time-to event will be shown. Graphic displays will also be used to summarize the data.

Participants who have taken at least one dose of JNJ-6379 during induction phase could be referred as being part of Trt-1 group and the other participants who have never taken JNJ-6379 as being part of Trt-2 group.

### 5.1.1. Level of Significance

Due to exploratory nature of this study, no formal test will be performed. Only two-sided 90% CIs will be provided.

### 5.1.2. Data Handling Rules

Those measurements collected from screening visit to the end of study will be handled according to the following rules summarized in Table 4.

**Table 4: Data Handling Rules for HBV Virology and Serology Assessments**

HBV parameter	LLOQ	ULOQ	Imputed Values	
			If value < LLOQ	If value > ULOQ
HBsAg	0.05 IU/mL	249,750.00 IU/mL with dilution	0.025 IU/mL (a)	274,725.00 IU/mL (b) with dilution
HBeAg	0.11 IU/mL	7,000.00 IU/mL with dilution	0.055 IU/mL (a)	7,700.00 IU/mL (b) with dilution
HBcrAg*	3.0 log 10 U/mL	7.0 log 10 U/mL w/o dilution 9.0 log 10 U/mL with dilution	2.7 log 10 U/mL	7.7 log 10 U/mL (b)(c) w/o dilution 9.9 log 10 U/mL (b) with dilution
HBV DNA	20 IU/mL	170,000,000 IU/mL w/o dilution	If target detected: 15 IU/mL If target not detected: 5 IU/mL**	187,000,000 (b)(c) IU/mL w/o dilution
HBV RNA*	LLOQ = 2.939 log 10 cp/mL (i.e., 869 cp/mL) LOD = 1.398 log 10 cp/mL	NAP	If <LOD or target not detected then 1.114 log 10 cp/mL (i.e., 13 cp/mL)	NAP

HBV parameter	LLOQ	ULOQ	Imputed Values	
			If value < LLOQ	If value > ULOQ
	(i.e., 25 cp/mL)			
Anti-HBs	5 mIU/mL	10000.0 mIU/mL	2.5 mIU/mL (a)	11000.0 mIU/mL (b)

\* As new assays become available different data handling rules may apply.

\*\* For HBV DNA <LLOQ: Spaghetti plots showing absolute values, the imputed value will be 15 IU/mL for both target detected and target not detected. All other tables, listings and figures, will be produced using 15 IU/mL as an imputed value if target is detected and 5 IU/mL if target is not detected.

Key: NAP=Not applicable

- (a) LLOQ/2
- (b) ULOQ+(ULOQ/10)
- (c) If the original result > ULOQ, then take the re-test value (i.e., diluted result). If the diluted result is not available, use the imputed value indicated in this table

All other viral activity data with values <LLOQ which are not included in the data handling rules above will be imputed by the absolute value divided by 2.

## 5.2. Primary Efficacy Endpoint

### 5.2.1. Definition

The primary efficacy endpoint, also known as “functional cure”, is the proportion of participants with HBsAg seroclearance 24 weeks after stopping all study interventions at the end of the consolidation phase and without restarting NA treatment.

### 5.2.2. Analysis Methods

All participants who do not achieve HBsAg seroclearance 24 weeks off-treatment during FU and/or require NA re-treatment within any time prior to FU Week 24 are considered treatment non-responders for the purpose of the primary endpoint analysis. The primary endpoint will be summarized with the point estimate and its 90% CI by using the Clopper-Pearson exact method by cohort.

#### 5.2.2.1. Missing Data Handling

Missing data will be handled with three approaches: observed data analysis, missing as non-responder, and LOCF.

##### 5.2.2.1.1. Observed Case Data

Participants who have missing HBsAg values at FU Week 24 will not be used for the analysis.

##### 5.2.2.1.2. Missing as Non-Responder

Participants who do not have HBsAg data in analysis window of FU Week 24 will be defined as non-responders.

### **5.2.2.1.3. Last Observation Carried Forward (LOCF)**

The third approach to handle missing data is based on the LOCF principle (single imputation). If the HBsAg value at FU Week 24 is missing and NA treatment has not been restarted, then LOCF in conjunction with the next available observation imputation will be applied. The available non-missing HBsAg value closest to the time point which is no earlier/later than 12 weeks prior/after to the FU Week 24 time point will be used. Participants who do not have data within the analysis window of  $\pm 12$  weeks around the FU Week 24 assessment will be defined as non-responders.

### **5.2.3. Subgroup Analyses of Primary Efficacy Endpoint**

The primary efficacy endpoint will be summarized descriptively using the number and percentage of participants by cohort by each subgroup of interest (Section 2.5.1).

### **5.2.4. Per-Protocol Analysis**

The analysis of the primary efficacy endpoint will be performed on the PP set, as defined in Section 2.3, using observed case data.

The proportion of responders will be summarized descriptively using the number and percentage of participants by cohort.

## **5.3. Secondary Endpoints**

See Section 1.1 for a list of the secondary endpoints.

### **5.3.1. Definitions**

#### **5.3.1.1. Binary Endpoints**

##### **5.3.1.1.1. Reaching HBsAg <10 IU/mL During the Induction Phase**

The participant has reached HBsAg <10 IU/mL at the end the induction phase, and the assessment will always be based on lab results.

##### **5.3.1.1.2. NA Treatment Completion Criteria**

###### **5.3.1.1.2.1. NA Treatment Completion Criteria During the Study**

NA treatment completion criteria are defined as follows:

- HBsAg <10 IU/mL, and
- HBeAg-negative (<LLOQ), and
- HBV DNA <LLOQ, and
- ALT <3x upper limit of normal [ULN]

The NA completion criteria will be assessed based on clinical laboratory tests and summarized at consolidation Week 12 and during FU phase.

### 5.3.1.1.2.2. NA Re-Treatment Criteria and Monitoring After Stopping of NA

Participants who meet the NA treatment completion criteria will be monitored closely during the follow-up phase.

After stopping NA treatment, participants should be monitored as follows:

- Regular monitoring visits will be every 4 weeks during the follow-up phase in accordance with the schedule of activities.
- A post-treatment HBV DNA value of >20,000 IU/mL should trigger re-testing of ALT/aspartate aminotransferase (AST), HBV DNA, and total and direct bilirubin within a maximum of 7 days from receipt of the data and further repeats as necessary (i.e., weekly until HBV DNA returns to <20,000 IU/mL).
- A post-treatment HBV DNA value of >2,000 IU/mL (but <20,000 IU/mL) should trigger a re-test within 14 days from receipt of the data and further repeats as necessary (i.e., every other week until HBV DNA returns to <2,000 IU/mL).
- A post-treatment ALT value of >5x ULN should trigger re-testing of ALT, AST, alkaline phosphatase (ALP), total and direct bilirubin, International Normalized Ratio (INR), albumin, and HBV DNA on a weekly basis until ALT and AST levels have returned to <5x ULN.

After stopping NA treatment, participants should re-start NA treatment:

- Immediately with signs of decreasing liver function based on laboratory findings (eg, INR, direct bilirubin) or clinical assessment (e.g., ascites, hepatic encephalopathy).
- Immediately with an HBV DNA value of >100,000 IU/mL (irrespective of confirmation and/or ALT increase).
- With confirmed post-treatment HBeAg seroreversion (HBeAg positive after it was negative at NA completion).
- With confirmed\* post-treatment increases in HBV DNA >2,000 IU/mL and ALT >5x ULN.
- With confirmed\* post-treatment increases in HBV DNA >20,000 IU/mL.

*\*At least 4 weeks apart – frequency of visits as described above.*

**Note:** Additional re-testing and/or earlier restarting of NA treatment is at the investigator's discretion, even if the above cut-offs are not yet met.

In case NA treatment is re-started, participants will be followed until the end of the study or until clinical stabilization, whichever comes later.

Participants who actually re-started NA treatment and monitoring after stopping of NA will be identified based on the 'Study Drug Administration for NA' CRF page.

Participants who meet the NA re-treatment criteria will be identified based on the CRF page of 'NA Re-treatment Criteria Assessment'.

### **5.3.1.1.3. HBsAg Sero clearance**

Sero clearance of HBsAg is defined as a (quantitative) HBsAg level <LLOQ. HBsAg sero clearance may be achieved prior to the time point assessed but must be observed at the given week of interest.

HBsAg sero clearance will be evaluated over all time points when assessed.

HBsAg sero clearance will be also evaluated when assessed at all time points after stopping all study interventions (regardless when intervention was stopped) and without restarting NA treatment.

If the HBsAg value at FU Week 12 is missing, the next available observation will be used. The next non-missing lab test no later than FU Week 24 will be imputed.

If the HBsAg value at FU Week 24 is missing, the LOCF in conjunction with the next available observation imputation approach will be used. The available non-missing lab test closest to FU Week 24 which is no earlier/later than 12 weeks from the actual time point of interest (FU Week 12 and FU Week 36, respectively) will be imputed.

If the HBsAg value at FU Week 36 is missing, the LOCF in conjunction with the next available observation imputation approach will be used. The available non-missing lab test closest to FU Week 36 which is no earlier/later than 12 weeks from the actual time point of interest (FU Week 24 and FU Week 48, respectively) will be imputed.

If the HBsAg value at FU Week 48 is missing, the LOCF will be used with the condition that no value earlier than FU Week 36 may be carried forward.

For all other time points, sero clearance will be analyzed as observed case without imputation.

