# 1.3.2. Schedule of Activities – Consolidation Phase and Follow-up Phase

**Note:** The last visit of the induction phase is equivalent to Day 1 of the consolidation phase. Refer to Section 1.3.1 Schedule of Activities Screening Phase and Induction Phase.

Note: During the follow-up phase, participants who could not stop NA at follow-up Week 2 will have less frequent visits.

Study Phase	Open-label Consolidation Phase						Follow-up a,b													
Consolidation (C)/ Follow up (FU) Week (W)	C W2	C W4	C W6	C W8	C W12 / EOSI / WD°	FU W2	FU W4	FU W8 d	FU W12	FU W16 d	FU W20 d	FU W24	FU W28 d	FU W32 d	FU W36	FU W40 d	FU W44 d	FU W48 / EOS		
C/FU Study Day (Window)	15 +/ 3d	29 +/ 3d	43 +/ 3d	57 +/ 3d	85 +/ 3d	15 +/ 4d	29 +/ 4d	57 +/ 4d	85 +/ 4d	113 +/ 4d	141 +/ 4d	169 +/ 4d	197 +/ 4d	225 +/ 4d	253 +/ 4d	281 +/ 4d	309 +/ 4d	337 +/ 4d		
Study Intervention																				
Administer JNJ 3989		X		X																
Intake of JNJ 6379 (if applicable) II	X	X	X	X																
Dispense of JNJ 6379 (if applicable) II		X		X																
Administer PegIFN α2ae		Wee	ekly																	
Dispense PegIFN α2ae		X		X																
Intake NA (as applicable) e,f	X	X	X	X	X	(X)	(X)	(X)	(X)	(X)	(X)	(X)	(X)	(X)	(X)	(X)	(X)	(X)		
Dispense NA (as applicable) f,g		X		X	X	(X)	(X)	(X)	(X)	(X)	(X)	(X)	(X)	(X)	(X)	(X)	(X)	(X)		
Study intervention accountability		X		X	X	(X)	(X)	(X)	(X)	(X)	(X)	(X)	(X)	(X)	(X)	(X)	(X)	(X)		
Assess NA re treatment criteria, as applicable g							(X)	(X)	(X)	(X)	(X)	(X)	(X)	(X)	(X)	(X)	(X)	(X)		
Safety Assessments																				
Complete physical examination h					X															
Body weight and Symptom directed physical examination	X	X	X	X		X	X	X	X	X	X	X	X	X	X	X	X	X		
Ophthalmic examinationii	(X)	(X)	(X)	(X)	(X)															
Injection site reactions for JNJ 3989 and PegIFN α2a	X	X	X	X	X															
Vital signs i	X	X	X	X	X	X	X	X	X	X	X	X	X	X	X	X	X	X		
Triplicate 12 lead ECG j					X		X													
Liver ultrasound					Xk							Xk						X		
Clinical Laboratory Tests																				
Renal biomarkers 					X															
Hematology m	X	X	X	X	X	X	X	X	X	X		X	X		X		X	X		
Blood chemistry (including liver function tests) n,o,p	X	X	X	X	X	X	X	Xq	X	Xq	Xq	X	Xq	Xq	X	X	X	X		
Blood coagulation		X		X	X	X	X		X			X			X		X	X		

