- a. All follow up study visits are to be scheduled relative to the last dose of JNJ 3989/PegIFN α2a. An unscheduled visit can be performed upon the investigator's discretion, in case of HBV DNA elevations, ALT elevations, other signs of worsening of liver disease, or for any other reason during follow up.
- Participants who withdraw consent during follow up will be offered an optional safety follow up visit.
- c. Participants who discontinue study intervention early will have an early WD visit and will enter follow up unless they withdraw consent. Participants who withdraw consent during study intervention will be offered an optional safety follow up visit to occur on the day of consent withdrawal. For the optional safety follow up visit, assessments are at the investigator's discretion and could be similar to the early WD visit.
- d. Follow up Week 8, 16, 20, 28, 32, 40, and 44 visits are not required for participants who did not complete NA treatment at Follow up Week 2 and for participants who have restarted NA treatment during the follow up period, provided that their HBV DNA and ALT values are stable.
- e. In between study visits, participants will take NA orally at home and will bring their NA with them to each study visit. At study visits, NA should be taken on site. PegIFN α2a should be administered weekly, preferably in the evening by self injection. If desired, participants can also choose to have the weekly administration of PegIFN α2a performed on site irrespective of the time of day. PegIFN α2a should preferably be administered in the evening prior to the sparse PK visit, or alternatively in the morning of the visit on site.

- f. No JNJ 3989/PegIFN α2a will be administered or dispensed during follow up. Administration/Dispensation of NA is only applicable for participants who could not stop NA treatment, or for those who met the NA re treatment criteria. In between study visits, participants will take NA at home and they will bring their NA treatment with them to each study visits, the NA treatment should be taken on site.
- g. If the NA treatment completion criteria are met at consolidation Week 12, treatment with NA will be completed at FU Week 2.
- h. Complete physical examination, including body weight, skin examination, and other body systems.
- i. Vital signs include supine SBP, DBP, pulse rate, and body temperature.

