The blood markers (such as HBsAg, HBeAg, HBV DNA, and ALT) during study intervention and follow-up will also be summarized by cohort over time and plotted. The proportion of participants with virologic breakthrough (on-treatment) and the proportion of participants with (sustained) reduction, suppression, and/or seroclearance during follow-up considering single and multiple markers (such as HBsAg, HBeAg, HBV DNA, and ALT) and various thresholds for the viral biomarker levels and/or changes from baseline will be summarized by cohort. The proportion of participants with HBsAg and HBeAg seroconversion will be tabulated by cohort. Descriptive statistics on values and changes from baseline over time in HBsAg, HBeAg and HBV DNA will be summarized by cohort.

The time to achieve first HBsAg and HBeAg seroclearance post randomization will be summarized, respectively, based on Kaplan-Meier estimates in tables and graphs.

The proportion of participants with HBsAg, HBeAg, and HBV DNA levels and/or changes from baseline below/above different cut-offs, will be analyzed as appropriate by cohort and over time. The proportion of participants who reach HBV DNA undetectability after re-start of NA treatment will be summarized by cohort.

Graphic data displays will also be used to summarize the efficacy data by cohort and over time.

Missing data for secondary and exploratory endpoints may be handled with a similar approach as the primary endpoint, adjusting the analysis window (e.g.,  $\pm 12$  weeks) for the specific time point as appropriate. If no data is available in the appropriate window for the given time point of interest then the imputation to non-response will be used in case of binary variables, and only observed cases for continuous variables.

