#### **5.3.1.1.6. Suppressed HBV DNA**

HBV DNA < LLOQ (HBV DNA detectable or HBV DNA TND) will be evaluated all time points when assessed after stopping all study interventions at the end of the consolidation phase and without restarting NA treatment.

HBV DNA < LLOQ (HBV DNA detectable or HBV DNA TND) will be also evaluated when assessed at all time points after stopping all study interventions (regardless when intervention was stopped) and without restarting NA treatment.

If the HBV DNA value at FU Week 12 is missing, the next available observation will be used. The next non-missing lab test no later than FU Week 24 will be imputed.

If the HBV DNA value at FU Week 24 is missing, the LOCF in conjunction with the next available observation imputation approach will be used. The available non-missing lab test closest to FU Week 24 which is no earlier/later than 12 weeks from the actual time point of interest (FU Week 12 and FU Week 36, respectively) will be imputed.

If the HBV DNA value at FU Week 36 is missing, the LOCF in conjunction with the next available observation imputation approach will be used. The available non-missing lab test closest to FU Week 36 which is no earlier/later than 12 weeks from the actual time point of interest (FU Week 24 and FU Week 48, respectively) will be imputed.

If the HBV DNA value at FU Week 48 is missing, the LOCF approach will be used with the condition that no value earlier than FU Week 36 may be carried forward.

For all other time points, HBV DNA will be analyzed as observed case without imputation.

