### **5.3.2.1.4. Suppressed HBV DNA**

The proportion of participants achieving HBV DNA <LLOQ (overall and separately for HBV DNA detectable and HBV DNA TND) will be summarized by cohort and analysis phase over time.

The proportion of participants with HBV DNA<LLOQ (overall and separately for HBV DNA detectable and HBV DNA TND) will be evaluated at each of the off-treatment time points,

respectively, after stopping all study interventions and without restarting NA treatment. In an additional summary, these proportions will be calculated with the denominator including only on those participants who have reached the off-treatment timepoint, and have stopped all interventions including NA and have not restarted NA prior to the timepoint of interest.

The proportion of participants who reach HBV DNA <LLOQ (overall and separately for HBV DNA detectable and HBV DNA TND) after restart of NA treatment during follow-up will also be tabulated by cohort.

The number of occurrences each subject has HBV DNA<LLOQ (overall and separately for HBV DNA detectable and HBV DNA TND) will be determined and summarized by cohort using frequency distributions and descriptive statistics. Additionally, the number of occurrences will be displayed graphically.

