### **5.3.2.2. Values and Change Over Time Endpoints**

#### **5.3.2.2.1. HBsAg, HBeAg, HBV DNA and ALT**

Descriptive statistics on actual values (original unit and  $\log_{10}$  transformed values), changes from baseline ( $\log_{10}$  transformed values), changes from consolidation reference time point ( $\log_{10}$  transformed values) over time in HBsAg, HBeAg, HBV DNA and ALT will be summarized by cohort and analysis phase. Mean (+/- SE) plots of the actual values, change from baseline ( $\log_{10}$  transformed) and change from consolidation reference time point ( $\log_{10}$  transformed) will be presented over time per blood marker by cohort and analysis phase.

In addition, the change from baseline value to the nadirs (i.e., maximum decrease for each participant) will be summarized descriptively by cohort. Box plots of the changes to nadir in HBsAg, HBeAg and HBV DNA will display the distribution by cohort.

Descriptive statistics on actual values (original unit and  $\log_{10}$  transformed values) and changes from baseline ( $\log_{10}$  transformed values) at end of consolidation in HBsAg, HBeAg, HBV DNA and ALT (original unit), respectively, will be summarized by cohort, by NA treatment completion criteria status at the end of consolidation phase, by functional cure status at FU Week 24 and 48, and for participants who achieved functional cure 24 weeks after stopping all study interventions regardless of meeting the NA completion criteria) and at the end of FU phase.

Cross-tabulations overtime and overall of quantitative versus qualitative HBsAg and HBeAg values, respectively, will also be presented.

Spaghetti plots for both absolute values and changes from baseline of HBsAg, HBeAg, HBV DNA and ALT will be presented over time (all data collected including unscheduled visit, all data within the same time interval, see [Section 2.1.3](#)) per blood marker by cohort and by selected subgroups (e.g. HBV Genotype), by NA treatment completion criteria status at the end of consolidation phase, by functional cure status at FU Week 24 and 48, and for participants who achieved functional cure 24 weeks after stopping all study interventions regardless of meeting the NA completion criteria) and at the end of FU, separately, will be presented graphically.

Shift tables in HBV DNA categories from baseline will also be summarized by cohort and analysis phase.

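### At seven of the 13 follow-up visits the by-cohort curves rest on a group selected by NA status, so they can move between visits with no participant changing status

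*SAP*

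**What the plan says.** **Visits.** The follow-up part of Protocol 1.3.2 lists 13 visits. A note there says that "participants who could not stop NA at follow-up Week 2 will have less frequent visits". Footnote d names FU Weeks 8, 16, 20, 28, 32, 40 and 44 and says that these "visits are not required for participants who did not complete NA treatment at Follow up Week 2 and for participants who have restarted NA" treatment, on condition that HBV DNA and ALT are stable. Six visits are left that everyone must attend: FU Weeks 2, 4, 12, 24, 36 and 48. NA is stopped only when HBsAg, HBeAg, HBV DNA and ALT all meet the completion criteria (Protocol 6.6.1).

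**Missing values.** SAP 5.3.1.1.3 fills in missing HBsAg at FU Weeks 12, 24, 36 and 48, and then states that seroclearance at any other time point "will be analyzed as observed case without imputation". SAP 5.3.1.1.6 does the same for HBV DNA: "For all other time points, HBV DNA will be analyzed as observed case without imputation". No missing-data rule is given for the threshold proportions or the mean curves. Protocol 9.4.1.2 outlines a different approach for secondary endpoints. It says that missing data may be handled as for the primary endpoint, with a nearest-value window adapted to the time point. If that window is empty, "then the imputation to non-response will be used in case of binary variables, and only observed cases for continuous variables".

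**Displays.** SAP 5.3.2.1.2, 5.3.2.1.4 and 5.3.2.1.5 tabulate seroclearance, HBV DNA below LLOQ and marker thresholds over time by cohort and analysis phase. SAP 5.3.2.2.1 adds "Mean (+/- SE) plots of the actual values, change from baseline" and change from the consolidation reference, again by cohort and phase. None of these is split by NA status. SAP 5.3.2.1.4 also counts per participant: "The number of occurrences each subject has HBV DNA<LLOQ".

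**The concern.** The weeks that footnote d makes optional all fall under the observed-case rule. Whether a participant has a value there depends on NA status and on the stability of HBV DNA and ALT, and both are tied to the markers being plotted. The people measured are those who stopped NA, those on NA who are unstable, and anyone else who chooses to come. That is not the cohort named on the table.

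A curve drawn through all 13 visits then mixes two populations and can zigzag for reasons of schedule alone. A reader could take this for loss or return of response after treatment. SAP Table 3 sends follow-up seroclearance over time to the quarterly data reviews, the second interim, the primary analysis and the final analysis, so several audiences would see it. The occurrence count for HBV DNA has a related flaw, because the number of scheduled follow-up opportunities differs by NA status.

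**Working it through.** **The plan's own figure.** The documents give no figure for the by-visit curves. The only stated precision is for 15 responders among 30: 33 × 0.9 = 29.7, taken as 30, with an exact 90% interval of 0.339–0.661 and width 0.322 (SAP 1.4, Protocol 9.2). The Clopper-Pearson formula reproduces it, and the same formula is used below.

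**Can the visit windows fill the gap?** No. Under SAP 2.1.3 each visit is assigned to one window and, apart from the end-of-phase visits, not used again. An FU Week 12 value therefore cannot also serve FU Week 8.

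**Illustration.** Assumptions:
- N = 30 and 6 stop NA. The protocol's Amendment 5 rationale cites 19.1% meeting the NA completion criteria in REEF-1, and 30 × 0.191 = 5.7. That regimen had no PegIFN, so this is a scenario only.
- 2 of the 6 stoppers clear HBsAg and no continuer does.
- HBV DNA is below LLOQ in 1/3 of stoppers and 90% of continuers.
- Mean log10 HBsAg is 0.5 in stoppers and 2.5 in continuers.
- Continuers who attend resemble those who do not.

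The outcome figures are assumed and have no source in the documents. With c continuers attending:
- seroclearance = 2/(6 + c)
- HBV DNA below LLOQ = (6 × 1/3 + 0.9c)/(6 + c)
- mean log10 HBsAg = (6 × 0.5 + 2.5c)/(6 + c)

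| c | Attendees | Seroclearance (90% CI) | HBV DNA <LLOQ | Mean log10 HBsAg |
|---|---|---|---|---|
| 0 | 6 | 33.3% (6.3–72.9) | 33% | 0.50 |
| 2 | 8 | 25.0% (4.6–60.0) | 48% | 1.00 |
| 6 | 12 | 16.7% (3.0–43.8) | 62% | 1.50 |
| 12 | 18 | 11.1% (2.0–31.0) | 71% | 1.83 |
| 24 | 30 | 6.7% (1.2–19.5) | 79% | 2.10 |

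The last row is a visit required of all. Moving between any other row and the last one is a shift with no change in any participant.

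**One stopper.** SAP Amendment 4 reports a single participant who met the criteria and stopped NA at consolidation Week 12. If that person clears, the observed-case rate is 1/1 = 100%, 1/4 = 25%, 1/8 = 12.5% or 1/15 = 6.7% with 0, 3, 7 or 14 continuers attending. Over all 30 it is 1/30 = 3.3% (0.2–14.9). If that person does not clear, the rate is 0 at every visit.

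**Occurrence count.** The schedule gives a stopper 13 follow-up visits and a stable continuer 6. A fully suppressed continuer can therefore score at most 6 at required follow-up visits, and a fully suppressed stopper 13.

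**The case against.** The case on the other side is substantial.

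- *Purpose of the displays.* The study tests no hypothesis, these are descriptive outputs, and the continuous summaries report n (SAP 5.1), so a drop in n is visible. This stands, and it limits the severity.
- *Other outputs already planned.* SAP 5.3.2.1.2 and 5.3.2.1.4 add summaries restricted to participants off all treatment, and SAP 5.3.2.2.1 plans spaghetti plots by NA-completion status. These are sound, but they sit beside the by-cohort proportions and means and do not correct them.

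Four stronger readings are tempting, and the documents do not support them.

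- *That the seven weeks show mainly the best responders and so look better.* The visits are optional, not cancelled, and unstable continuers must still attend. With the one reported stopper, a few continuers would outnumber that person, and unstable ones could pull the result the other way.
- *That the SAP contradicts the protocol.* Protocol 9.4.1.2 is permissive, takes the nearest value in a window before non-response, and prescribes observed cases for continuous variables. The mean curves therefore follow it. It contains no rule that counts participants on NA as non-responders.
- *That HBV DNA suppression always looks worse.* The illustrated fall applies only to the general over-time table in SAP 5.3.2.1.4. For the endpoint off treatment without NA restart, a participant on NA cannot be a responder, so that person's absence cannot lower the rate.
- *That the main durability results are biased.* FU Weeks 24 and 48 are required of everyone and have their own missing-data rules.

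**Conclusion.** The concern holds as a defect of intermediate descriptive displays. At 7 of 13 follow-up visits, the by-cohort seroclearance, HBV DNA, threshold and mean results describe a group selected by NA status and stability. The schedule and the observed-case rule establish this without any assumption about outcomes.

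The size and direction of the distortion cannot be derived from the documents, because they give no attendance by NA status. The figures above show what is possible under stated assumptions. The shift shrinks as more continuers attend and vanishes at full attendance. The FU Week 24 primary endpoint, the FU Week 48 endpoints and the restricted-denominator off-treatment summaries are not touched. The change is worth making because it is cheap, but it is not a must-fix.

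**What to change.** Amend SAP 5.3.1.1.3, 5.3.1.1.6, 5.3.2.1 and 5.3.2.2:

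1. Show by-cohort follow-up proportions and mean plots only at FU Weeks 2, 4, 12, 24, 36 and 48.
2. At FU Weeks 8, 16, 20, 28, 32, 40 and 44, show results split by NA status (stopped; continued or restarted) with n at each visit. Keep the continuers who attend.
3. If by-cohort binary proportions are kept at those seven weeks, use the full analysis-set denominator, take the nearest value in the window, and then apply non-response, as Protocol 9.4.1.2 outlines. Each of the seven weeks lies 4 weeks from a required visit, so a nearby value will usually exist. For endpoints off treatment without NA restart, state that participants on NA count as non-responders. This follows from the endpoint definition, not from 9.4.1.2.
4. Report the count of HBV DNA results below LLOQ over the common visits only.

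The cost is SAP wording and table shells, with no new data and no change to visits. The downside is fewer points on the by-cohort curves and very small groups at the seven weeks, possibly a single stopper.
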